2.4.4.4.5 Analysis of anosmia category

For UPSIT, number (%) of patients with anosmia will be summarized for dupilumab 300mg q2w and placebo, respectively, at baseline and Week 24.

The anosmia category is defined as:

- 0-18 anosmia
- 19-25 severe microsmia
- 26-30 moderate microsmia
- 31-34 mild microsmia
- 35-40 normal

2.4.4.5 Analyses of exploratory efficacy endpoints

2.4.4.5.1 Analyses of efficacy endpoints for Arm B versus placebo at Week 52

The change from baseline in LMK, TSS, UPSIT, daily assessed loss of smell, VAS for overall rhinosinusitis, EQ-5D utility and daily assessed severity of rhinorrhea at Week 52 and percent change from baseline in NC, TSS, daily assessed loss of smell and VAS for overall rhinosinusitis at Week 52 will be assessed separately for dupilumab 300 mg q2w/q4w (Arm B) versus placebo and will be analyzed using the hybrid method of the WOCF and the MI in the same fashion as for the key secondary endpoints of change from baseline in NC, in NPS and SNOT-22 at Week 52. Descriptive statistics including number of patients, mean, standard error, and least squares (LS) means will be provided. In addition, difference in LS means and the corresponding 95% confidence intervals (CI) will be provided along with the p-values.

For responder type endpoints including

- The proportion of patients with improvement by at least 1 point in NPS and 0.5 reductions in NC at Week 52

The Cochran-Mantel-Haenszel test will be performed on the association between the responder status and treatment group, stratified by asthma/NERD status, prior surgery history, and region. Comparisons of the proportions of responders between dupilumab 300mg q2w/q4w (Arm B) and

placebo will be derived. And corresponding odds ratios and 95% CI will be reported. Patients who are indicated for surgery for NP or receive SCS for any reason will be considered as non-responders for time points after using SCS or surgery. For patients who discontinue treatment without using SCS or surgery, data collected during the off-treatment period will be used to determine the responder/non-responder status. Missing data at Week 52 will be considered as non-responders.

2.4.4.5.2 Other exploratory analyses

Total SCS dose prescribed (in mg) during the study period and total SCS intake in days and courses during the study period will be summarized by treatment groups. A course of SCS is considered continuous if treatment is separated by less than 7 days. Various doses of systemic corticosteroids will be converted to prednisone-equivalent oral corticosteroid. For patients who discontinue treatment, data collected during the off-treatment period will also be used. Descriptive statistics including number of subjects, mean, standard deviation, min, and max will be provided, and no statistical testing will be conducted.

Proportion and time-to-event of patients requiring rescue treatment with SCS for any reason, SCS for nasal polyps, SCS for respiratory disease, and surgery (planned or actual) for NP will also be performed using the same method as those for the secondary endpoint of the proportion of patients requiring rescue with SCS or NP surgery (actual or planned) during the treatment period for dupilumab 300 mg q2w versus placebo using the pooled data of the two NP studies SINUS-52 (EFC14280) and SINUS-24 (EFC14146).

Change from baseline in decreased/loss of sense of taste symptom severity and SNOT-22 items: "decreased sense of smell/taste", "difficulty falling asleep", "wake up at night", "lack of a good night's sleep", "wake up tired", "fatigue", and "reduced productivity", (FEV1, FVC and FEF25-75 in patients with asthma) at Week 24 and Week 52 will be assessed separately. For analyses at Week 24, dupilumab 300 mg q2w (Arm A and first 24 weeks of Arm B) versus placebo will be analyzed using the hybrid method of the WOCF and the MI in the same fashion as for the primary analysis for co-primary endpoints at Week 24. For analyses at Week 52, dupilumab 300 mg q2w (Arm A) and dupilumab 300 mg q2w/q4w (Arm B) versus placebo and will be analyzed using the hybrid method of the WOCF and the MI in the same fashion as for the key secondary endpoints of change from baseline in NC, in NPS and in SNOT-22 at Week 52. Descriptive statistics including number of patients, mean, standard error, and least squares (LS) means will be provided. In addition, difference in LS means and the corresponding 95% confidence intervals (CI) will be provided.

2.4.4.6 Missing data handling

For all continuous efficacy endpoints, the details of missing data handling are described in [Section 2.4.4.1](#).

For responder type endpoints, the details of missing data handling are described in [Section 2.4.4.2](#).

In addition, the reason and pattern of missing data will be carefully examined and pattern mixture modeling approach and other sensitivity analyses will also be performed as specified in [Section 2.4.4.1](#).

2.4.5 Analyses of safety data

The summary of safety results will be presented by treatment group.

General common rules

All safety analyses will be performed on the safety population as defined in [Section 2.3.2](#), unless otherwise specified, using the following common rules:

- The baseline value is defined as the last available value before the first dose of IMP.
- The potentially clinically significant abnormality (PCSA) values are defined as abnormal values considered medically important by the Sponsor according to predefined criteria/thresholds based on literature review and defined by the Sponsor for clinical laboratory tests, vital signs, and ECG [[Appendix A](#)]
- PCSA criteria will determine which patients had at least 1 PCSA during the treatment-emergent adverse event period, taking into account all evaluations performed during the treatment-emergent adverse event period, including nonscheduled or repeated evaluations. The number of all such patients will be the numerator for the on-treatment PCSA percentage
- The treatment-emergent PCSA denominator by group for a given parameter will be based on the number of patients assessed for that given parameter in the treatment-emergent adverse event period by treatment group on the safety population.
- For quantitative safety parameters based on central laboratory/reading measurements, descriptive statistics will be used to summarize results and change from baseline values by visit and treatment group. Summaries will include the endpoint value and/or the worst on-treatment value. The endpoint value is commonly defined as the value collected at the end of treatment. If this value is missing, this endpoint value will be the closest value prior to the end of treatment epoch. The worst value is defined as the nadir and /or the peak post-baseline (up to the end of treatment epoch or EOT) according to the direction (minimum or maximum) of the abnormality as defined in the PCSA list
- The analysis of the safety variables will be essentially descriptive and no systematic testing is planned. Relative risks versus placebo and their 95% confidence intervals may be provided, if relevant
- All safety values including unscheduled measurements will be assigned to the appropriate safety analysis visit window defined in [Section 2.5.3](#).

2.4.5.1 Analyses of adverse events

Generalities

The primary focus of adverse event reporting will be on treatment-emergent adverse events. Pretreatment and posttreatment adverse events will be described separately.

If an adverse event date/time of onset (occurrence, worsening, or becoming serious) is incomplete, an imputation algorithm will be used to classify the adverse event as pretreatment, treatment-emergent, or posttreatment. The algorithm for imputing date/time of onset will be conservative and will classify an adverse event as treatment emergent unless there is definitive information to determine it is pretreatment or posttreatment. Details on classification of adverse events with missing or partial onset dates are provided in [Section 2.5.2](#).

Adverse event incidence tables will present by SOC, HLG, HLT, and PT, sorted in alphabetical order for each treatment group, the number (n) and percentage (%) of patients experiencing an adverse event. Multiple occurrences of the same event in the same patient will be counted only once in the tables within a treatment phase. The denominator for computation of percentages is the safety population within each treatment group.

Sorting within tables ensures the same presentation for the set of all adverse events within the observation period (pretreatment, treatment-emergent, and posttreatment). For that purpose, the table of all treatment-emergent adverse events presented by SOC and PT sorted by the internationally agreed SOC order and decreasing frequency of PTs within SOCs will define the presentation order for all other tables unless otherwise specified. Sorting will be based on results for the dupilumab 300 mg q2w group.

Analysis of all treatment-emergent adverse events

The following treatment-emergent adverse event summaries will be generated for the safety population.

- Overview of treatment-emergent adverse events, summarizing number (%) of patients with any
 - Treatment-emergent adverse event
 - Serious treatment-emergent adverse event
 - Treatment-emergent adverse event leading to death
 - Treatment-emergent adverse event leading to permanent treatment discontinuation
- All treatment-emergent adverse event by primary SOC, HLG, HLT, and PT, showing number (%) of patients with at least 1 treatment-emergent adverse event sorted by the SOC internationally agreed order. The other levels (HLG, HLT, PT) will be presented in alphabetical order
- Number (%) of patients experiencing TEAE(s) presented by PT, sorted by decreasing incidence of PT

- All treatment-emergent adverse events by primary SOC and PT, showing the number (%) of patients with at least 1 treatment-emergent adverse event, sorted by the internationally agreed SOC order and by decreasing incidence of PTs within each SOC in the 300 q2w treatment group
- All treatment-emergent adverse events regardless of relationship and related by primary SOC, HLGT, HLT and PT, showing the number (%) of patients with at least 1 treatment-emergent adverse event, sorted by the internationally agreed SOC order. The other levels (HLGT, HLT, PT) will be presented in alphabetical order
- All treatment-emergent adverse events by maximal severity, presented by primary SOC and PT, showing the number (%) of patients with at least 1 treatment-emergent adverse event by severity (ie, mild, moderate, or severe), sorted by the internationally agreed SOC order and by decreasing incidence of PTs within each SOC in the 300 q2w treatment group
- Number (%) of patients experiencing treatment-emergent adverse event(s) presented by primary and secondary SOC, HLGT, HLT, and PT sorted by the internationally agreed SOC order. The other levels (HLGT, HLT, PT) will be presented in alphabetical order

A listing of all treatment-emergent adverse events will be presented

Analysis of all treatment emergent serious adverse event(s)

- All treatment-emergent serious adverse events by primary SOC, HLGT, HLT, and PT, showing the number (%) of patients with at least 1 serious treatment-emergent adverse event, sorted by the internationally agreed SOC order. The other levels (HLGT, HLT, PT) will be presented in alphabetical order
- All treatment-emergent serious adverse events regardless of relationship and related to IMP, by primary SOC, HLGT, HLT, and PT, showing the number (%) of patients with at least 1 treatment-emergent serious adverse event, sorted by the internationally agreed SOC order. The other levels (HLGT, HLT, PT) will be presented in alphabetical order
- All treatment-emergent serious adverse events by primary SOC and PT, showing the number (%) of patients with at least 1 treatment-emergent serious adverse event, sorted by the internationally agreed SOC order and by decreasing incidence of PTs within each SOC in the 300 q2w treatment group.

A listing of all treatment-emergent serious adverse events will be presented

Analysis of all treatment-emergent adverse event(s) leading to treatment discontinuation

- All treatment-emergent adverse events leading to treatment discontinuation, by primary SOC, HLGT, HLT, and PT, showing the number (%) of patients sorted by the internationally agreed SOC order. The other levels (HLGT, HLT, PT) will be presented in alphabetical order
- All treatment-emergent adverse events leading to permanent treatment discontinuation or drug interruption, by primary SOC and PT, showing number (%) of patients with at least one TEAE, will be presented by SOC internationally agreed order and by decreasing incidence of PTs within each SOC in the 300 q2w treatment group.

Analysis of adverse events of special interests (AESI) and other selected AE groupings

- All treatment-emergent adverse events, by selected standardized MedDRA query (SMQ) and PT or by laboratory values (as in ALT elevation), showing the number (%) of patients with at least 1 PT, sorted by decreasing incidence of PTs within each SMQ in the 300 q2w treatment group.
- For each AESI and other selected AE groupings,
 - Number (%) of patients with any specific TEAE
 - Number (%) of patients with any specific serious AE (regardless of treatment emergent status)
 - Number (%) of patients with any specific treatment emergent serious AE
 - Number (%) of patients with any specific AE leading to death
 - Number (%) of patients with any specific TEAE leading to permanent study drug discontinuation
 - Number (%) of patients with any specific TEAE by maximum intensity, corrective treatment, and final outcome
 - Number of any specific TEAE adjusted by the exposure duration
 - Number of patients with any specific TEAE adjusted by the exposure duration at risk. For each specific TEAE, Kaplan-Meier estimates of cumulative incidence at Week 12, 24, 36 and 52 and K-M plot may be provided to depict the course of onset over time if the number of events is large enough.
 - Number (%) of patients with injection site reactions by the related injection.
 - Number (%) of patients with different number of injection site reactions.
- In addition, AESIs reported by the investigator in CRF will be summarized separately.

Analysis of treatment-emergent adverse events up to Week 24

- Selective safety analyses will be performed on safety data from baseline to Week 24 with respect to TEAE, SAE, TEAE leading to permanent treatment discontinuation or drug interruption, AE adverse events of special interests (AESI) and other selected AE groupings.
- ***Analysis of pretreatment adverse events*** All pretreatment adverse events by primary SOC and PT, showing the number (%) of patients with at least 1 pretreatment adverse event, sorted by the internationally agreed SOC order and decreasing incidence of PTs within each SOC in the 300 q2w treatment group.
- All serious pretreatment adverse events by primary SOC and PT, showing the number (%) of patients with at least 1 pretreatment adverse event, sorted by the internationally agreed SOC order and decreasing incidence of PTs within each SOC

- All pretreatment adverse events leading to permanent treatment discontinuation by primary SOC and PT, showing the number (%) of patients, sorted by the internationally agreed SOC order and decreasing incidence of PTs within each SOC
- All pretreatment adverse events leading to death by primary SOC and PT, showing the number (%) of patients, sorted by the internationally agreed SOC order and decreasing incidence of PTs within each SOC
- If only a few patients have pretreatment adverse events leading to permanent treatment discontinuation, a listing will be presented instead of the summary table above.

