2.1.4 Safety endpoints

The safety analysis will be based on the reported adverse events and other safety information, such as clinical laboratory data, vital signs, ECG and physical examination.

Observation period

The observation period will be divided into 4 epochs:

- The **screening** epoch is defined as the time from the signed informed consent date up to the time prior to first administration of the IMP.

- The **treatment** epoch is defined as the time from the first administration of the IMP to the last administration of the IMP + 14 days.
- The **residual treatment** epoch is defined as the time from the last administration of the IMP +15 days to the last administration of the IMP + 98 days.

The treatment-emergent adverse event period will include both **treatment** and **residual treatment** epochs.

- The **posttreatment** epoch is defined as the period of time starting the day after the end of the treatment-emergent adverse event period up to the end of the study (defined as last protocol planned visit or the resolution/stabilization of all serious adverse events and adverse events with pre-specified monitoring).
- The on-study observation period is defined as the time from start of treatment until the end of the study (defined as last protocol planned visit or lost to follow-up or the resolution/stabilization of all serious adverse events and adverse events with pre-specified monitoring).

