2.1.4.1 Adverse events variables

Adverse event observation period

- Pretreatment adverse events are adverse events that developed or worsened or became serious during the screening epoch
- Treatment-emergent adverse events are adverse events that developed or worsened or became serious during the treatment-emergent adverse event period
- Posttreatment adverse events are adverse events that developed or worsened or became serious during the posttreatment epoch

All adverse events (including serious adverse events and adverse events with pre-specified monitoring/of special interests) will be coded to a lower-level term (LLT), preferred term (PT), high-level term (HLT), high-level group term (HLGT), and associated primary system organ class (SOC) using the version of Medical Dictionary for Regulatory Activities (MedDRA) currently in effect at Sanofi at the time of database lock.

The occurrence of adverse events (including serious adverse events and adverse events with prespecified monitoring) will be recorded from the time of signed informed consent until the end of the study. **Adverse events of special interest (AESI) and other selected AE groupings** will be searched based on the criteria in [Table 1](#).

Table 1 Criteria for adverse events of special interest and other selected AE groupings

AE Grouping	Criteria
AESI	
Anaphylactic reaction	Anaphylactic reaction algorithmic approach (Introductory Guide for Standardised MedDRA Queries (SMQs) Version 18.1): includes anaphylactic reaction narrow SMQ (20000021) terms; for selection based on occurrence of multiple symptoms, the symptoms must have occurred within 24 hours of each other
Hypersensitivity (medically reviewed)	SMQ hypersensitivity (20000214) narrow search and [AE corrective treatment/therapy='Y' or Action taken with IMP='Drug withdrawn' or Action taken with IMP='Drug interrupted'] followed by blinded medical review (documented process) for selection of relevant systemic hypersensitivity events
Serious injection site reactions or severe injection site reactions that last longer than 24 hours	HLT = 'Injection site reaction' and either with serious status, or with severe status and (AE end date/time - AE start date/time) ≥ 24 hours or ongoing
Severe or serious infection	Primary SOC = 'Infections and infestations' and with severe or serious status
Parasitic infection	The Infection Type 'Parasitic' was checked on eCRF page "Infection Defined as AESI Complementary Form"

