2.4.3.1 Extent of investigational medicinal product exposure

The extent of IMP exposure will be assessed by the duration of IMP exposure.

Duration of IMP exposure is defined as last dose date – first dose date + 14 days, regardless of unplanned intermittent discontinuations (see [Section 2.5.3](#) for calculation in case of missing or incomplete data). Duration of IMP exposure will be summarized descriptively as a quantitative

variable (number, mean, SD, median, minimum, and maximum). In addition, duration of treatment exposure will also be summarized categorically by numbers and percentages for each of the following categories and cumulatively according to these categories:

- >0 and ≤ 2 weeks
- >2 and ≤ 4 weeks
- >4 and ≤ 8 weeks
- >8 and ≤ 12 weeks
- >12 and ≤ 16 weeks
- ...
-
- >48 and ≤ 52 weeks
- >52 weeks

Additionally, the cumulative duration of treatment exposure will be provided, defined as the sum of the duration of treatment exposure for all patients, and will be expressed in patient years.

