2.5.3 Missing data

For categorical variables, patients with missing data are not included in calculations of percentages unless otherwise specified. When relevant, the number of patients with missing data is presented.

Handling of computation of treatment duration if investigational medicinal product end of treatment date is missing For the calculation of the treatment duration, the date of the last dose of IMP is equal to the date of last administration reported on the end-of-treatment case report form page. If this date is missing, the exposure duration should be left as missing.

The last dose intake should be clearly identified in the case report form and should not be approximated by the last returned package date.

Handling of medication missing/partial dates

No imputation of medication start/end dates or times will be performed. If a medication date or time is missing or partially missing and it cannot be determined whether it was taken prior or concomitantly, it will be considered a prior, concomitant, and posttreatment medication.

Handling of adverse events with missing or partial date/time of onset

Missing or partial adverse event onset dates and times will be imputed so that if the partial adverse event onset date/time information does not indicate that the adverse event started prior to treatment or after the treatment-emergent adverse event period, the adverse event will be classified as treatment-emergent. No imputation of adverse event end dates/times will be performed. These data imputations are for categorization purpose only and will not be used in listings. No imputation is planned for date/time of adverse event resolution.

Handling of adverse events when date and time of first investigational medicinal product administration is missing

When the date and time of the first IMP administration is missing, all adverse events that occurred on or after the day of randomization should be considered as treatment-emergent adverse events. The exposure duration should be kept as missing.

The last dose intake should be clearly identified in the case report form and should not be approximated by the last returned package date.

Handling of missing assessment of relationship of adverse events to investigational medicinal product

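### The event-based AESI rate counts events to 98 days after the last dose but divides by exposure that ends at 14 days, overstating it by 0% to about 25%

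*SAP*

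**What the plan says.** SAP 2.1.4.1 sets the numerator: "Treatment-emergent adverse events are adverse events that developed or worsened or became serious during the treatment-emergent adverse event period". SAP 2.1.4 sets that period: "The treatment-emergent adverse event period will include both" the treatment epoch and the residual treatment epoch, and the latter runs "to the last administration of the IMP + 98 days". Protocol 11.3.2 agrees, ending the treatment-emergent period at Week 12 of the post-treatment period.

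SAP 2.4.3.1 gives the only definition of exposure: "Duration of IMP exposure is defined as last dose date – first dose date + 14 days". Protocol 11.4.1.1 has the same formula. SAP 2.4.3.1 also sums this quantity over patients into patient-years, the only person-time total in the SAP. SAP 2.5.3 uses the term in the same sense when the last dose date is unknown: "If this date is missing, the exposure duration should be left as missing".

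SAP 2.4.5.1 then asks, for each AESI and other selected grouping, for two adjusted measures:
- an event-based one, "Number of any specific TEAE adjusted by the exposure duration";
- a patient-based one, whose denominator is called exposure duration *at risk*. That term is not defined anywhere.

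Neither item refers back to SAP 2.4.3.1.

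**The concern.** A rate needs events and person-time from the same window. A programmer who follows the SAP will take the one exposure duration it defines and divide into it events from a window that is 84 days longer. Events in the residual epoch enter the numerator while the days in which they arose do not enter the denominator.

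At stake are the absolute adjusted rates for groupings such as infections, hypersensitivity and conjunctivitis, which readers may set beside rates from other studies. The SAP separates the two windows elsewhere: SAP 2.4.2 summarises concomitant medication to last dose + 14 days and to last dose + 98 days in separate tables. SAP 2.4.5.1 makes no such distinction.

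**Working it through.** The documents state no adjusted rate or person-time total, so there is no figure to reproduce. The inputs are:
- last planned dose at Week 50, or 350 days after the first (SAP 1.4.1);
- exposure ends at last dose + 14 days (SAP 2.4.3.1);
- event counting ends at last dose + 98 days (SAP 2.1.4);
- the final analysis uses data up to a lock taken when all patients have completed Week 52 or discontinued (SAP 4);
- 25% dropout, a sample-size assumption (SAP 1.3), used here only to set a range.

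**Completer.** Exposure is 350 + 14 = 364 days (Week 52). The counting window is 350 + 98 = 448 days (Week 64). These match the end-of-treatment and end-of-study visits. The ratio is 448/364 = 1.23.

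**Early stoppers, full follow-up.** The ratio is (last dose day + 98)/(last dose day + 14):
- last dose Week 38: 364/280 = 1.30
- Week 24: 266/182 = 1.46
- Week 16: 210/126 = 1.67
- Week 8: 154/70 = 2.20

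**General formula.** Let E be mean exposure days, R mean observed residual days, and r the event rate in the residual epoch divided by that in the treatment epoch. Relative to the on-treatment rate, the printed rate is too high by 1 + r × R/E.

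Assumptions for the range:
- Of all patients, 0% or 25% stop, uniformly over the dosing period. With 25%, E = 0.75 × 364 + 0.25 × (175 + 14) = 320.25 days.
- Accrual is uniform over A days. The documents do not give its length. The lock then leaves completers a mean of 84 × (1 − 42/A) residual days: 42.0 for A = 84 and 74.3 for A = 365. Stoppers are credited with all 84.

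| Setting | r = 0 | r = 0.5 | r = 1 |
|---|---|---|---|
| Full follow-up, none stop | 1.00 | 1.12 | 1.23 |
| Full follow-up, 25% stop | 1.00 | 1.13 | 1.26 |
| Lock, A = 84, none stop | 1.00 | 1.06 | 1.12 |
| Lock, A = 84, 25% stop | 1.00 | 1.08 | 1.16 |
| Lock, A = 365, none stop | 1.00 | 1.10 | 1.20 |
| Lock, A = 365, 25% stop | 1.00 | 1.12 | 1.24 |

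If the benchmark is instead the rate over the whole treatment-emergent period, the factor is (E + R)/E whatever r is. That is the r = 1 column.

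**Between arms.** Suppose 25% stop on placebo and 10% on dupilumab, with a mean exposure of 112 days among stoppers (all assumed), full follow-up and r = 1. Placebo: E = 0.75 × 364 + 0.25 × 112 = 301, factor 385/301 = 1.279. Dupilumab: E = 0.90 × 364 + 0.10 × 112 = 338.8, factor 422.8/338.8 = 1.248. The ratio is 1.025. With r = 0.5 it is 1.140/1.124 = 1.014.

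**The case against.** **The denominator is inferred.** SAP 2.4.5.1 does not point to SAP 2.4.3.1 and gives no unit. That is true, but no other exposure duration is defined, and SAP 2.5.3 uses the term for the same quantity. If another quantity was meant, it is missing from the SAP and the same edit is needed.

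**A reader might infer that every adjusted rate is wrong.** The documents do not support that. The patient-based rate has its own undefined denominator, and nothing shows that it stops at 14 days. The selective Week 24 safety analyses use data only to Week 24, so the residual window does not enter for patients still on treatment then.

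**A reader might infer a fixed inflation of a quarter.** As an error in the on-treatment rate, that needs an unchanged event rate for 84 days off drug and complete follow-up. Injection-site reactions follow injections, so few new ones should arise in the residual epoch. The Week 52 lock truncates that epoch for late-enrolled completers, and patients who withdraw from the study may not supply it at all. The lock does not help for earlier stoppers: under Protocol 10.3.1, those who discontinue before Week 40 and stay in follow-up report adverse events through Week 52, which covers all 98 days for a last dose up to Week 38.

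**A reader might infer a bias between arms.** Unequal discontinuation is an assumption here, and even a 25% versus 10% split moves the ratio by only 1.4% to 2.5%.

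**Consequences are limited.** SAP 2.4.5 calls the safety analysis essentially descriptive. The number-and-percentage tables and the optional Kaplan-Meier estimates are unaffected, and the error overstates risk rather than hiding it. All of this stands, but it does not make the event-based rate right.

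**Conclusion.** As written, the event-based AESI rate in SAP 2.4.5.1 pairs a numerator window ending at last dose + 98 days with person-time ending at last dose + 14 days. For a fully followed completer with a constant event rate the overstatement is 23%. Against the on-treatment rate it runs from 0% to about 25% at cohort level, provided that the residual event rate is no higher than the on-treatment rate. The accrual length and stopping pattern behind that range are assumed. Individual early stoppers contribute a larger mismatch. Absolute rates are affected far more than between-arm ratios. For the patient-based rate the documents show a missing definition, not an error. This should be corrected before database lock, but it does not touch the main safety tables.

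**What to change.** In SAP 2.4.5.1, define person-time for the event-based rate as first dose to the earliest of last dose + 98 days, last contact or data cut-off. For the patient-based rate, use the same interval and end it also at the patient's first event in the grouping. This matches numerator and denominator for completers, early stoppers and patients truncated by the lock.

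The cost is a sentence or two in the SAP, a small programming change and lower stated rates: for a fully followed completer, 364/448 = 0.81 of the figure that the current text would give. For groupings tied to injections the matched rate averages in off-drug time, so it should be labelled as a rate over the treatment-emergent period.

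Keeping the 14-day exposure and counting only treatment-epoch events would also match the windows. It is the weaker choice, because the event count behind the rate would then differ from the treatment-emergent counts in the same table and residual-epoch events would drop out of the rate.
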